### 6.4 Concomitant Medication

All concomitant medication should be appropriate as determined by the treating physician and should be documented in the CRF. For instance, at the discretion of the treating physician, broad-spectrum antibiotics may also be given to cover possible superimposed bacterial infections.

### 6.5 Follow-up

Collection from daily recordings will be undertaken either prospectively or retrospectively to assess adverse event and efficacy of therapy from day 1 (1st day of treatment) to day 10 and then weekly while admitted to the treatment centre and then 30 days post last dose. For patients for whom therapy is discontinued prior to day 10, assessments will follow the same schedule to allow comparison of disease course.

The following will be recorded, as permitted, starting immediately prior to the onset of administration of IFN  $\beta$ -1a, then on a daily basis whilst the patient is in the treatment centre:

- Temperature; fever will be defined as a temperature  $\geq 38$  °C.
- Concurrent illness symptoms: chills, myalgia, cough, sore throat, nausea, vomiting, diarrhea, hemaorrhage.
- Adverse events will be recorded per protocol. Medication history at baseline and daily will be recorded.
  - Blood samples:
    - 20 cc of Blood for virologic measurement (if feasible).
    - A convalescent serum (10 cc tiger top tube) will be obtained at 1 month (when possible).
  - Survival

Of note, it is expected that there will be missing data points for study participants depending on the clinical care data available in the medical chart and residual blood samples available for testing.

## **7. Clinical Pharmacology of IFN $\beta$ -1a**

### **7.1 Pharmacodynamics**

Interferons (IFNs) are a family of naturally occurring proteins, produced by eukaryotic cells in response to viral infection and other biologic agents. Three major types of interferons have been defined: type I (IFN-alpha, beta, epsilon, kappa and omega), type II (IFN-gamma) and type III (IFN-lambda). Interferon-beta is a member of the type I subset of interferons. The type I interferons have considerably overlapping but also distinct biologic activities. The bioactivities of all IFNs, including IFN-beta, are induced via their binding to specific receptors on the surface of human cells. Differences in the bioactivities induced by the three major subtypes of IFNs likely reflect differences in the signal transduction pathways induced by signaling through their cognate receptors.

Interferon beta exerts its biological effects by binding to the IFNAR1 and IFNAR2 receptors on the surface of human cells. This binding initiates a complex cascade of intracellular events that leads to the expression of numerous interferon-induced gene products and markers. These include 2', 5'-oligoadenylate synthetase,  $\beta_2$ -microglobulin, and neopterin. These products have been measured in the serum and cellular fractions of blood collected from patients treated with IFN  $\beta$ -1a.

Clinical studies conducted in multiple sclerosis patients showed that interleukin 10 (IL-10) levels in cerebrospinal fluid were increased in patients treated with IFN  $\beta$ -1a compared to placebo. Serum IL-10 levels maximally were increased by 48 hours after intramuscular injection of IFN  $\beta$ -1a and remained elevated for 1 week. However, no relationship has been established between absolute levels of IL-10 and clinical outcome in multiple sclerosis.

### **7.2 Pharmacokinetics**

Pharmacokinetics of AVONEX in multiple sclerosis patients has not been evaluated. The pharmacokinetic and pharmacodynamic profiles of IFN  $\beta$ -1a in healthy subjects following doses of 30 mcg through 75 micrograms have been investigated. Serum levels of IFN  $\beta$ -1a as measured by antiviral activity are slightly above detectable limits following a 30 mcg subcutaneous dose, and increase with higher doses.

After a subcutaneous dose, serum levels of IFN  $\beta$ -1a generally peak at 15 hours post-dose (range: 6-36 hours) and then decline at a rate consistent with a 19 (range: 8-54) hour elimination half-life.

Biological response markers (e.g., neopterin and  $\beta_2$ -microglobulin) are induced by IFN  $\beta$ -1a following parenteral doses of 15 micrograms through 75 micrograms in healthy subjects and treated patients. Biological response marker levels increase within 12 hours of dosing and remain elevated for at least 4 days. Peak biological response marker levels are typically observed 48 hours after dosing. The relationship of serum IFN  $\beta$ -1a levels or levels of these induced biological response markers to the mechanisms by which IFN  $\beta$ -1a exerts its effects in multiple sclerosis is unknown.

### **7.3 Description of Pharmaceutical IFN $\beta$ -1a Single-Use Prefilled Syringe**

A prefilled syringe of IFN  $\beta$ -1a is a sterile liquid for injection. Each 0.5 mL of 60 mcg/mL of IFN  $\beta$ -1a in a prefilled glass syringe contains 30 mcg of IFN  $\beta$ -1a, 0.79 mg Sodium Acetate Trihydrate, USP; 0.25 mg Glacial Acetic Acid, USP; 15.8 mg Arginine Hydrochloride, USP; and 0.025 mg Polysorbate 20 in Water for Injection, USP at a pH of approximately 4.8.

A dose titration device will be supplied by Biogen Idec that will enable a half dose (0.25 mL = 15  $\mu$ g = 3 million IU) to be administered from the full dose syringe if dose reduction is required.

## **8. Management of Ebola Disease Progression, Adverse Events and Serious Adverse Events**

### **8.1 Ebola Disease Progression**

It is expected that the disease will continue to progress for the initial 24-72 hours of therapy. Stabilization or improvement is not anticipated to manifest until day 3-5. Considering the potential adverse events of IFN  $\beta$ -1a therapy, special consideration will be placed to determine whether the treatment regimen adversely affects disease progression.

If the participant progresses at  $\geq 48$  hours while being treated with IFN  $\beta$ -1a in terms of worsening of disease symptoms and if this progression is felt by the treating physician to probably be related to the treatment regimen, then IFN  $\beta$ -1a will be either decreased in dose or discontinued.

### **8.2 Adverse Events Management**

It is expected that IFN  $\beta$ -1a will have a direct antiviral effect if initiated early in the course of illness and will have an immunomodulatory effect on exaggerated inflammatory responses observed in ill patients. It is likely that this drug will cause certain flu-like symptoms or symptoms compatible with disease progression but it is unlikely that these symptoms will be serious with the short 10-day-course. If there is concern that IFN  $\beta$ -1a is associated with worsening of disease, it may be dose-reduced or treatment stopped.

#### **Adverse Events**

This section is extracted from the product monograph and is supplementary information to that provided in section 2.3 of the protocol. The side effects listed are based on a phase 3 study with 9 or 15  $\mu$ g of IFN  $\beta$ -1a given three times a week for 24-48 weeks. Since IFN  $\beta$ -1a is given for 10 days in this study, the safety information, listed in section 2.3 for 10 days of therapy, may be more relevant.

The most common adverse events of AVONEX reported in placebo-controlled studies (IM administration) are listed below with the incidence in placebo-treated multiple sclerosis patients listed first and AVONEX-treated multiple sclerosis patients listed second: headache (55%, 58%), flu-like symptoms (29%, 49%), pain (21%, 23%), asthenia (18%, 24%), fever (9%, 20%), chills (5%, 19%), abdominal pain (6%, 8%), injection site pain (6%, 8%), infection (4%, 7%), injection site inflammation (2%, 6%), chest pain (2%, 5%), injection site reaction (1%, 3%), toothache

(1%, 3%), depression (14%, 18%), dizziness (12%, 14%), upper respiratory tract infection (12%, 14%), sinusitis (12%, 14%), bronchitis (5%, 8%), nausea (19%, 23%), myalgia (22%, 29%), arthralgia (6%, 9%), urinary tract infection (15%, 17%), urine constituents abnormal (0%, 3%), alopecia (2%, 4%), eye disorder (2%, 4%), injection site ecchymosis (4%, 6%), anemia (1%, 4%), migraine (3%, 5%), vasodilation (0%, 2%). As some of these symptoms may occur following virus infection, it may be difficult to know whether they are due to the administration of IFN  $\beta$ -1a or the patient's underlying condition

### **Rare Adverse Events (<1% frequency)**

Severe psychiatric adverse events may develop in persons receiving therapy with IFN  $\beta$ -1a and includes suicidal ideation and suicide. The risk of this happening is small and less than 1%.

IFN- $\alpha/\beta$  has on occasion exacerbated pre-existing cardiovascular disease, and has caused angina (chest pain), rhythm disturbances or heart attacks (myocardial infarction) in these persons. In those with known pre-existing heart disease, physicians will monitor for cardiac symptoms closely and discontinue IFN  $\beta$ -1a if cardiovascular symptoms appear to be worsened by the drug.

IFN  $\beta$ -1a has rarely been associated with ophthalmic problems, including retinal hemorrhages, optic neuritis and papilledema in persons on long-term treatment. Participants will be asked to report to their physician any disturbance in vision while they are on treatment.

IFN  $\beta$ -1a may exacerbate liver disease and will be discontinued with grade 4 hepatotoxicity.

Very rarely IFN  $\beta$ -1a has been associated with pulmonary syndromes including pneumonia and worsening of asthma. If a participant develops worsening pulmonary symptomatology, which is felt to be due to IFN  $\beta$ -1a then the drug will be dose-reduced or stopped.

IFN  $\beta$ -1a may aggravate autoimmune diseases (for example, systemic lupus or rheumatoid arthritis), and those with pre-existing autoimmune disease will be closely monitored.

### **Management of Adverse Events**

Management of adverse events is generally achieved by dose reduction of IFN  $\beta$ -1a, however, in the case of life-threatening adverse events, development of cardiac dysfunction, or precipitous decline in pulmonary function over a 24 hour period, which is not explained by disease progression and which may be associated IFN  $\beta$ -1a, therapy will be discontinued.

Flu-like symptoms can be treated with acetaminophen 500-1000 mg or ibuprofen 200-400 mg 30 minutes before IFN  $\beta$ -1a injection.

The following guidelines will be used to determine when dose modification of the investigational product for an adverse event should be implemented.

- Grade I (mild) adverse events: No dosage adjustment
- Grade 2 (moderate) adverse events: No dosage adjustment
- Grade 3 (severe) adverse events: Patients who develop grade 3 adverse events (except flu like symptoms, unless they are incapacitating) should have IFN  $\beta$ -1a reduced to 3 MIU (15 mcg). Alternatively, IFN  $\beta$ -1a may be discontinued.

- Grade 4 (Life threatening) adverse events (SAE): IFN  $\beta$ -1a will be discontinued.

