### 6.3 Treatment Schedule

IFN  $\beta$ -1a will be obtained from BiogenIdec Inc., Cambridge, MA 02142, USA. The dosage will be as follows: 6 million IU SC  $\times$  10 days. Administration should follow the product monograph, and will generally be done by the patient's nurse while in the treatment centre.

The IFN  $\beta$ -1a dose may be decreased if there are problems with tolerance by 3 million IU (15  $\mu$ g) to 3 million IU. Once it is well tolerated, the dose may remain the same or may be re-increased by 3 million IU to a maximum of 6 million IU/30  $\mu$ g per day. Dose adjustments are under the treating physician responsibility.

The duration of treatment may be shorter than 10 days in cases where the patient recovers more rapidly, with a minimum of 7 days therapy. The decision to stop IFN  $\beta$ -1a therapy in such cases will be made by the patient's treating physician. In general, patients are expected to discontinue treatment upon discharge from the treatment centre or about 48 hours prior to discharge for observation of deterioration of treatment. Most patients are expected to be admitted at least 7 days due to the nature of the illness. If any patient needs to discontinue prior to day 7 of therapy, the rationale will be documented on a case-by-case basis.

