## 12. Premature Discontinuation of Treatment

Participants may withdraw from the study at any time for any reason without jeopardy to their current or future care. The investigator may also withdraw patients from the study without the participant's permission in the event of intercurrent illness, adverse events, treatment failures, protocol violation, administrative reasons, or any other reasons. The reason for withdrawal should be clearly documented in the CRF.

Specific criteria for premature discontinuation of treatment will also include, progression of disease due to IFN  $\beta$ -1a or grade IV adverse events felt to be due to IFN  $\beta$ -1a. If the reason for removal of a patient from the study is an adverse event or abnormal laboratory result, the

principal specific event or test will be documented completely on the CRF. A participant will be withdrawn if at any time, in the opinion of the investigator, study participation would not be in the best interest of the participant.

Participants may withdraw or be withdrawn from treatment and this will not automatically lead to withdrawal from the rest of the study. These participants would continue to be followed per protocol for safety and disease course, off therapy. Unnecessary withdrawal of patients should be avoided.

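### The Section 8.2 dose-change list stops IFN β-1a for grade 4 events whatever their cause, while the text above it and Section 12 look to a link with the drug

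*Protocol*

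**What the plan says.** The list in Section 8.2 (Management of Adverse Events) is introduced with "The following guidelines will be used to determine when dose modification of the investigational product for an adverse event should be implemented". Its grade 4 item, "Grade 4 (Life threatening) adverse events (SAE", leads to discontinuation. Its grade 3 item begins "Patients who develop grade 3 adverse events (except flu like symptoms, unless they are incapacitating) should have IFN" β-1a reduced to 3 MIU, with discontinuation as the alternative. Grades 1 and 2 call for no change. No item mentions cause. Section 8.3 then defines an adverse event so that no causal link with the product is needed.

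Other places make the link with the drug part of the decision:

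- The paragraph directly above the list discontinues therapy for life-threatening events, cardiac dysfunction or rapid pulmonary decline, "which is not explained by disease progression and which may be associated IFN" β-1a.
- The opening paragraph of Section 8.2 allows reduction or stopping where there is concern that the drug is associated with worsening disease.
- Section 8.1 reduces or stops the drug for progression at 48 hours or later if "this progression is felt by the treating physician to probably be related to the treatment regimen".
- Section 12 includes among its discontinuation criteria "grade IV adverse events felt to be due to IFN" β-1a.

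Section 6.3 sets the regimen at 6 million IU daily for 10 days and makes dose adjustment the treating physician's responsibility.

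**The concern.** Life-threatening events caused by Ebola while on drug are foreseeable. Section 1.1 gives high fatality, and Section 8.1 expects the disease to keep progressing over the first 24 to 72 hours of therapy. For such an event judged to be Ebola and not drug, the list calls for stopping. The paragraph above it and the Section 12 criterion do not supply that trigger. Two physicians following the same protocol could manage the same patient in opposite ways.

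If the list is followed literally, the sickest patients receive the least drug, so exposure depends on prognosis. The primary endpoint in Section 9.1 is the change in viral RNA from day 1 to day 10, and Section 16 rests the decision to extend on safety and a trend toward efficacy. A null viral-load result would then be harder to read: the drug may not work, or it may have been withdrawn early from those with the highest burden of disease.

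**Working it through.** The plan gives no figure on this point, so there is none to reproduce. The check is a comparison of the rules, followed by a bound on how many patients they could affect.

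**Step 1. One case under each rule.** Take a grade 4 event on treatment that the physician attributes to Ebola alone.

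| Place | Condition on cause | Does it call for stopping? |
|---|---|---|
| Section 8.2, list | none | yes |
| Section 8.2, paragraph above the list | not explained by disease, possibly drug | no (if the qualifier covers life-threatening events) |
| Section 8.2, opening paragraph | concern about association with the drug | no |
| Section 8.1 (progression at 48 hours or later) | probably related to the regimen | no |
| Section 12, grade IV criterion | judged due to the drug | no |

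If the list applies whatever the cause, the attribution qualifiers for grade 4 events have no work to do. If the qualifiers govern, the list omits them.

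**Step 2. Grade 3.** Section 12 is silent on grade 3, and Section 8.1 and the opening of Section 8.2 speak of progression or worsening without grades. The list reduces or stops without regard to cause. Its flu-like exemption is by type of symptom, not by cause. The conflict at this grade is indirect.

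**Step 3. Scale.** Inputs: planned size N = 30 to 50 (Section 10.1); fatality p = 57-90% (Section 1.1); cumulative deaths and cases (Section 1.2, Table 1). Assumption: every fatal case has a grade 4 event while on drug. Number stopped by the list = N × p.

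- 30 × 0.57 = 17.1; 30 × 0.90 = 27.
- 50 × 0.57 = 28.5, rounded to 29; 50 × 0.90 = 45.

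Crude ratios from Table 1:

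- Guinea: 1214/2047 = 0.593, giving 17.8 of 30 and 29.7 of 50.
- Liberia: 2963/7082 = 0.418, giving 12.6 of 30 and 20.9 of 50.
- Sierra Leone: 1267/6190 = 0.205, giving 6.1 of 30 and 10.2 of 50.

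These are upper bounds for fatal cases, because some deaths fall after treatment ends. Survivors with a life-threatening event are not counted, and the protocol gives no figure for them.

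**Step 4. The attribution wording.** The protocol gives no share of grade 4 events that would be attributed to the drug. Call it q; the number stopped is N × p × q. For illustration only, with p = 57-90%: q = 0 gives none; q = 0.10 gives 1.7 to 2.7 of 30 and about 2.9 to 4.5 of 50; q = 0.25 gives about 4 to 7 of 30 and 7 to 11 of 50. At q = 1 the two wordings coincide. The gap is therefore material unless most Ebola complications would be attributed to the drug.

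**The case against.** The best defence is context. The list follows a description of the drug's side effects and sits under a paragraph that mentions attribution. It is called a guideline, and Section 6.3 leaves dosing to the physician. Section 8.1 handles disease progression separately, so Ebola shock could be thought to fall there and not under the list. These readings soften the conflict. They do not remove it, because the list states its own action without condition, Section 8.3 defines adverse events broadly enough to include Ebola complications, and nothing says that Section 8.1 takes precedence. The qualifier above the list might also attach only to pulmonary decline. In that case the list agrees with the paragraph above it and the conflict with Section 12 remains.

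Several stronger readings are tempting but unsupported:

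- **Every grade 3 or 4 event triggers a change.** Grade 3 flu-like symptoms are exempt unless incapacitating.
- **Section 6.3 contradicts the grade 2 item.** The clause "dose may be decreased if there are problems with tolerance" is permissive, names no grade and is not an attribution test. Set beside "Grade 2 (moderate) adverse events: No dosage adjustment" it is loose, and a cross-reference is enough.
- **Section 12 gives no ground to stop in Ebola shock.** Its criteria are introduced as additional, not exclusive. It also lets the investigator withdraw patients from the study for adverse events or any other reason, and requires withdrawal when participation is not in the patient's interest.
- **The results become uninterpretable.** Section 6.5 keeps the same assessment schedule after an early stop, Section 12 continues follow-up off therapy, and no analysis by dose received is described.

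**Conclusion.** The contradiction stands. It is direct at grade 4, between the list on one side and the Section 12 criterion and (on its natural reading) the paragraph above the list on the other. At grade 3 it is indirect. Its possible reach is large: up to about 17 to 27 of 30 or 29 to 45 of 50 patients at the fatality in Section 1.1, or about 6 to 18 of 30 or 10 to 30 of 50 at Table 1's crude ratios. Both ranges assume that every fatal case has a grade 4 event on drug. They describe literal use of the list and do not forecast what physicians would do. The number stopped under the attribution wording cannot be derived from the document.

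The harm is inconsistent patient management and exposure that follows prognosis, which weakens the reading of a null viral-load result. Outcome collection is not lost. This should be fixed, but it does not invalidate the trial. No view is taken here on which clinical rule is right.

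**What to change.** Reconcile Section 8.1, the opening paragraph of Section 8.2, the paragraph above the list, the list itself and the Section 12 criterion into one dose-change rule, with a cross-reference from Section 6.3. The rule should state whether attribution applies at each grade and, if so, which test is used. The sponsor and treating physicians choose its content.

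In the CRF, record the day, the grade and the attributed cause for every reduction and re-increase as well as every stop. Much of this is already collected: adverse events and their causal assessment (Section 8.3), reasons for withdrawal (Section 12) and the rationale for stopping before day 7 (Section 6.3). What is missing is mainly the link between each dose change and its grade and cause.

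The cost is protocol wording and a few CRF fields, with no extra patients or visits.

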### 8.3 Adverse Event Definitions and Reporting

Adverse Event (AE): is any untoward medical occurrence in a patient or clinical investigation participant administered a product. It does not necessarily have to have a causal relationship with this treatment. An AE can therefore be any unfavorable and unintended sign (including an abnormal laboratory finding, for example), symptom or disease temporally associated with the use of a medicinal product, whether or not considered related to the medicinal product.

All adverse events will be recorded and transcribed into the CRF. Solicited AEs and non-solicited AEs will be collected daily for the first four days and then every 2-3 days during therapy, or whenever reported by patients. SAEs will be collected while on study medication and for 30 days after administration of the last dose.

**Serious Adverse Event (SAE):** is any adverse event that:

- is fatal
- is life-threatening
- results in persistent or significant disability/incapacity
- requires initial hospitalization or prolongation of existing hospitalization
- causes congenital anomalies or birth defects

The term "life-threatening" refers to an event in which the patient was at risk of death at the time of the event. It does not refer to an event, which hypothetically might have caused death, if it were more severe. All deaths occurring while on protocol therapy or within 30 days of the last dose, should be reported (see below).

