### **5. Study Design**

This study is single-arm clinical trial with a pre- and post- study design. The study will include patients who are admitted with EBOV infection to a treatment centre. If a patient meets the inclusion criteria and gives informed consent (or informed consent is given by a substitute decision maker who is responsible for the patient due to the patient's illness), the patient will be enrolled into the study i.e. the first 30-50 eligible patients will be enrolled. Patients who receive IFN  $\beta$ -1a will be treated through the Special Access/Compassionate Release Program (consent to treatment through their treating physician) administered in Conakry, Guinea. This part of the study will collect data retrospectively, including results from research testing of (residual/to be discarded) blood samples. The study team can make available the systematic data collection forms to the treating physician to help in monitoring of adverse events and effect of therapy, enabling more specific reporting to the Special Access Program administered in Conakry, Guinea by the treating physician for patients receiving IFN  $\beta$ -1a.

As noted above, retrospective data collection will include patients with EBOV disease who do not participate in this clinical trial. Data from IFN  $\beta$ -1a-treated patients will be matched with data from patients who did not receive IFN  $\beta$ -1a, based on age, sex, estimated days post-onset of symptoms, and viral load (if available). This data collection is similar to that proposed in this protocol. Also, this protocol proposes to test blood collected clinically (residual or to be discarded) for comparisons between the groups in this interventional study.

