### **6.1 Informed Consent Process**

#### **Clinical Trial:**

All participants (or substitute decision makers) must understand and sign the informed consent document. The Guinean physicians and associated health workers will play an important role in addressing cultural and ethical sensitivities associated with the treatment protocol, and the Guinean authorities have indicated they will assume responsibility for disseminating information about the nature of clinical trials aimed at treating Ebola virus disease.

The observational part of the study will collect data retrospectively, and results from research testing of (residual/to be discarded) blood samples and respiratory secretions.

The comparison group for this part of the study will in part be the population that may be included in an existing epidemiologic study for which there is a waiver of consent. For patients

in the comparison group who were not enrolled in such a study where waiver of consent was applied, all reasonable efforts will be made to obtain informed consent where that individual's data will be used. However, it should be noted that obtaining informed consent from a non-IFN  $\beta$ -1a-treated patient who survived the ebola infection and left the clinic may be difficult to obtain, as it may be from the relatives of those non-IFN  $\beta$ -1a-treated patients who died following ebola infection. Retrospective data collection and testing will be as consistent as possible with the clinical trial data collection form, depending on data available from medical records. Research testing will be performed on the blood and secretions samples (residual or to be discarded).

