### 9.2 Secondary

**Safety:** Occurrence and severity of adverse event; time to onset, duration (number of days), severity, and seriousness of solicited and non-solicited injection site reactions and systemic adverse events occurring up to 7 days after the last injection. Occurrence, nature, time to onset relative to the first IFN  $\beta$ -1a dose, duration, severity, relationship to injection of SAEs throughout the trial.

- The frequency of clinically important (moderate or severe) adverse events will be compared between the groups
- The frequency of serious adverse events will be compared between the groups.

Parameters to look for adverse events will be solicited such as local injection site erythema and swelling, fever, heart rate, blood pressure, and rash.

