## 11. Data Management

All data management, including the design of the CRFs, design of the database, as well as data entry and assurance of data integrity will be assumed by the Investigators or delegates. The CRFs, if possible, will be appended to a participant's clinical chart for direct documentation by the treating physician(s) and nurses. This plan is to accommodate data collection and transcription in the context of limited resources during this outbreak.

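### Adverse event collection is scheduled around IFN dosing while comparators have only retrospective records, so the planned AE and SAE comparison is biased toward apparent harm on IFN to the extent that comparator events are missed

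*Protocol*

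**What the plan says.** **IFN patients.** Section 8.3 states: "Solicited AEs and non-solicited AEs will be collected daily for the first four days and then every 2-3 days during therapy". It continues: "SAEs will be collected while on study medication and for 30 days after administration of the last dose". Section 9.2 sets the AE window as "systemic adverse events occurring up to 7 days after the last injection" and lists injection-site erythema and swelling among the solicited items. The AE definition in 8.3 itself presupposes treatment: "any untoward medical occurrence in a patient or clinical investigation participant administered a product". Section 11 asks that CRFs be attached, where this can be done, to a participant's "clinical chart for direct documentation by the treating physician(s) and nurses".

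**Comparators.** Section 5 says that "retrospective data collection will include patients with EBOV disease who do not participate in this clinical trial". Section 6.1 promises collection as close to the trial form as can be managed, but "depending on data available from medical records". No section gives comparators a solicitation schedule, an AE or SAE window, or a contact after discharge.

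**The comparison.** Section 9.2 compares moderate or severe AEs between the groups and adds: "The frequency of serious adverse events will be compared between the groups". Section 8.4 calls for direct comparison of treated and untreated patients. Section 10.2 assigns Fisher's exact test to categorical endpoints and counts the presence of any event as well as of any related event. Section 16 makes safety a determining factor for extending the study.

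**The concern.** A between-group difference in recorded events mixes two things: how often events happen, and how often they are found. Here the finding process is written around the drug. Someone asks the IFN patient about symptoms at set contacts and looks for SAEs after discharge. For the comparator, an event counts only if routine care happened to chart it.

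The effect is not confined to events judged related to treatment. It also reaches the all-cause counts, which 9.2 compares and 10.2 analyses as presence of any event. A test on those counts cannot separate a real harm from more thorough looking. A false signal could weigh against extension, and a real one could be put down to detection. A later analysis plan could narrow the comparison, but it could not recover comparator events that nobody asked about or charted.

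**Working it through.** **1. There is no figure in the plan to reproduce.** Section 10.1 gives 30-50 as a feasibility number, without alpha, power, event rates or a comparator group size. Everything below is illustration.

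**2. The two groups side by side.**

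| Feature | IFN | Comparator |
|---|---|---|
| AE solicitation | Scheduled during therapy (8.3) | None stated |
| AE window | To 7 days after last injection (9.2) | None stated |
| SAE window | To 30 days after last dose (8.3) | None stated |
| Source | Study form in chart where possible (11); data prospective or retrospective (6.5) | Retrospective, from medical records (5, 6.1) |

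**3. Formula for AEs.** Observed rate = true risk × probability of recording. The true risk is set equal in both groups, so the drug is harmless and any expected difference is true risk × (IFN capture − comparator capture).

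**4. Assumptions, none from the protocol.** True risk of a moderate or severe AE 50% or 70%; 1:1 groups of 30 or 50; Fisher's exact test, two-sided 5%. Rejection probabilities come from summing the binomial probabilities of all tables with p ≤ 0.05.

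| Capture, IFN v comparator | Observed at true 50% | Observed at true 70% | Rejection, n=30 | Rejection, n=50 |
|---|---|---|---|---|
| Equal (100% in both) | 50 v 50% | 70 v 70% | 2.6-2.7% | 3.1-3.5% |
| 90 v 80% | 45 v 40% | 63 v 56% | 3.8-4.9% | 5.6-7.9% |
| 90 v 75% | 45 v 37.5% | 63 v 52.5% | 5.3-8.2% | 8.6-14.4% |
| 80 v 60% | 40 v 30% | 56 v 42% | 7.8-13.1% | 13.2-24.1% |
| 100 v 80% | 50 v 40% | 70 v 56% | 7.7-13.3% | 13.4-23.9% |
| 100 v 60% | 50 v 30% | 70 v 42% | 25.9-49.6% | 46.3-77.0% |

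In each row the lower figure belongs to the 50% risk, apart from the equal-capture row, where it belongs to 70%. With unequal capture nearly all rejections go against IFN. For example, at 90 v 75%, 70% risk and n=30, 8.1 of the 8.2 points do.

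**5. SAEs.** Section 6.3 allows 7 to 10 days of dosing, so the IFN window ends at about day 37 to 40. If comparators leave on day 7 to 14 (assumption), the unobserved share of that window is between (37 − 14)/37 = 62% and (40 − 7)/40 = 82.5% of days. That is a share of days, not of events. Suppose instead that in-centre SAEs occur in 50% of patients and are fully charted in both groups, and that a further 5, 10 or 20% of patients have their first SAE after discharge, recorded only on IFN (assumptions). A significant excess on IFN then appears in 3.4, 7.5 or 25.9% of trials at n=30, and in 5.4, 13.3 or 46.3% at n=50.

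**The case against.** The contrast is softer than Section 8.3 alone suggests. Sections 5 and 6.5 allow IFN data to be collected retrospectively too, and missing data are openly expected. The study form goes into the chart only where possible. Section 5 describes comparator collection as similar to the protocol's, with matching on days since onset, and 6.1 asks for consistency with the trial form. Section 6.2 counts by day of hospitalization and of illness for treated and untreated alike, and 10.2 analyses AEs in periods ending at day 10. Some comparators may come from an existing epidemiologic study with its own collection. For SAEs, Section 1.1 quotes 57-90% fatality, and deaths in the centre should be charted in either group. Follow-up of early-discharged IFN patients at one month is itself conditional (6.2).

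This all stands, and it limits the size. It does not remove the problem. A shared form cannot recover symptoms that were never asked about. The common day count and AE periods align timing but not detection, and they do not replace the dose-based SAE window.

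A reader might infer that the comparison will show excess harm from a harmless drug. The documents do not support that. They give no capture rates, and even at 100 v 60% with 30 per group, about half or more of trials would show no significant difference. Nor are injection-site reactions evidence of detection bias: they are real effects of injection. They simply have no counterpart in an untreated patient.

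It is also fair that this is a feasibility pilot, that the stopping rule in 8.4 rests on a treatment-related death rather than on this comparison, and that Section 16 sets no test or threshold.

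**Conclusion.** The point holds as a directional bias of unknown size. AE solicitation and both event windows are defined only by IFN dosing. Comparators have retrospective records and no matching schedule or window, yet all-cause frequencies are to be compared directly. If comparator capture is less complete, the comparison leans toward harm on IFN.

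Modest gaps in capture raise the false-positive rate only somewhat above its value under equal capture; large gaps raise it severely. The upper figures require full capture on IFN, which the protocol's own expectation of missing data makes doubtful. All figures assume equal true risk and 1:1 groups. The SAE part of the bias lies mainly after discharge.

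The restriction in 8.4 to AEs attributable to the intervention is a separate difficulty, since an untreated patient cannot have one; the bias described here does not depend on it.

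**What to change.** In Sections 8.4, 9.2 and 10.2, limit the between-group AE and SAE comparison as follows:

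- **Events:** a fixed list that can be abstracted from routine clinical records, using the same form in both groups, without injection-site terms.
- **Source:** flag where each event was found. Do not count entries that appear only on an appended study CRF or arose only from study solicitation; otherwise chart abstraction would bring the study-driven recording back in.
- **Time:** use the drug-independent day count of 6.2, from the index day to day 10 while in the centre.
- **Exposure:** report events with the days observed in each group, for example per patient-day, so that unequal stay does not distort the comparison.

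Report solicited events, injection-site reactions and events after discharge for the IFN group only, descriptively. State that residual detection bias limits the comparison. Safety collection and SAE reporting for IFN patients stay as they are.

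The cost is protocol wording, one source field on the CRF and a count of days observed. The downside is that fewer IFN events enter the comparison, though all are still reported. The source flag should be in place before data collection, because it cannot be reliably reconstructed later.
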